4.2 Exclusion criteria

- History of biopsy-proven acute rejection
- Presence of donor-specific antibodies (at any MFI)
- Spot urine protein/creatinine ratio > 0.5 g/g

4.3 Selection of participants

Belatacept-treated single kidney transplant recipients will be recruited from the outpatient clinic. Eligible patients are preselected through review of medical records. They are informed of the possibility to participate by a physician (the co-investigator, who is not their own nephrologist) at the time of an outpatient clinic. They will be given a copy of the informed consent and asked to call the co-investigator if they are interested in participating.

4.4 Withdrawal of subjects

Subjects will be withdrawn from the trial in case of:

- Refusal of the subject to continue
- For any other reason deemed necessary by the investigator and in the interest of the subject.

In the following circumstances, subjects will continue to be monitored in the study but immunosuppression will not be weaned further:

- Either one of the immune monitoring tests are positive at any point (Allosure > 1% or Trugraf signature compatible with rejection)
- Occurrence of biopsy-proven acute rejection (Banff 2017 criteria)
- Occurrence of new proteinuria > 0.5 g/g creatinine, confirmed on repeat urine sample after 2-4 weeks
- Occurrence of de novo donor-specific antibodies at any MFI
- Decrease in eGFR > 20% from baseline without alternative explanation, confirmed on repeat urine sample after 2-4 weeks

5. Trial Procedures

5.1 By visit

For all belatacept-treated patients, monthly visits in the outpatient clinic, where belatacept infusions are administered, are part of routine clinical care. Trial visits will coincide with these infusion visits, occurring monthly for the first year after inclusion. At study visits, subjects are questioned and examined by a physician and blood samples are drawn (see below). For patients who receive monthly belatacept infusions at home, they will have blood samples (clinical and research specimens) drawn at their local Quest laboratory and the study physician will call them to assess for adverse events. If any adverse events are noted, a telemedicine or in-person visit with a transplant nephrologist will be scheduled at the discretion of the investigator.

Reduction of immunosuppression occurs in a stepwise fashion, whereby each reduction is contingent on several factors:

- Renal function is stable, defined as eGFR no more than 20% lower compared to value at inclusion
- Both the Allosure and Trugraf tests indicate a state of immune quiescence. For the Allosure, this corresponds to a dd-cfDNA concentration of < 1%; for the Trugraf test, this corresponds to a "TX" signature.
- No appearance of any de novo DSA (at any MFI) at any previous point during study
- No proteinuria > 0.5 g/g creatinine on spot urine sample

If, at any point, a patient does not fulfill all of the abovementioned criteria, immunosuppression will not be (further) reduced. In such cases, the principal investigator will decide whether to continue with the reduced-intensity immunosuppressive regimen or revert back to conventional triple therapy (belatacept + mycophenolate/mTORi + steroids).

Criteria for performing a kidney biopsy are:

- Unexplained decrease in eGFR > 40% from baseline value
- Occurrence of new proteinuria > 1.0 g/g creatinine on 2 separate random urine samples

The principal investigator can decide to perform a kidney biopsy in patients who do not strictly meet the abovementioned criteria, if the probability of rejection is felt to be high, i.e. a combination of abnormalities such as new DSA and proteinuria < 1 g/g, or a very high (>3%) Allosure result combined with a mild (20%) decrease in eGFR.

In case of a discrepancy between Allosure and Trugraf results (i.e. Allosure < 1% but Trugraf positive for rejection), immunosuppression will not be weaned further.

Study timeline

Time point	Blood sample including immune monitoring	Urine protein	DSA monitoring	Action if stable renal function, immune quiescence, no de novo DSA, no proteinuria > 0.5 g/g
Inclusion	Yes	Yes	Yes	
Month 1	Yes	Yes		50 % reduction of MMF/mTORi dose
Month 2	Yes			
Month 3	Yes		Yes	
Month 4	Yes	Yes		Stop MMF/mTORi
Month 5	Yes			
Month 6	Yes		Yes	
Month 7	Yes	Yes		Reduction in prednisone to alternating 5mg – 2.5mg
Month 8	Yes			Reduction in prednisone to 2.5mg
Month 9	Yes		Yes	Reduction in prednisone to 2.5mg – 0mg alternating
Month 10	Yes			Stop steroids
Month 11	Yes			
Month 12	Yes	Yes	Yes	

From months 13 through 24, subjects will resume routine (standard of care) clinical monitoring, namely monthly laboratory analyses when they get their belatacept infusion. In addition to this, proteinuria and DSA will be checked at 24 months (which is not standard of care).

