5.2 Laboratory testing and sample shipping

The following laboratory tests are performed at each study visit during the first 12 months:

- Routine laboratory analyses, including complete blood count, basic metabolic panel, total protein, fasting glucose. These analyses will be performed by the Central Laboratory of Massachusetts General Hospital or at the patient's local Quest laboratory.
- Two 10 ml Streck Cell-Free DNA BCT® whole blood tubes are drawn and stored at 7°C pending shipment. Streck tubes are shipped at ambient temperature (between 6° and 37°C) to CareDx using the shipping material and instructions provided by CareDx.
- Two 2.5ml Paxgene® whole blood tubes are drawn and stored at -20°C pending shipment. These tubes are shipped on ice (-20°C) to Transplant Genomics.
- One 10 ml EDTA and one 10 ml SST tube will be collected, centrifuged at 4°C for 10 minutes at 3000 RPM. The resulting 5 ml of EDTA plasma and 5 ml of SST plasma will be stored at -80°C pending possible future analysis (i.e. biobanked).

Donor-specific antibody screening occurs at 1, 4, 7, 10, 12 and 24 months. These analyses will be performed by the HLA laboratory of Massachusetts General Hospital.

6. Statistics

Normality will be tested using the Shapiro-Wilk test. Average eGFR and proteinuria at baseline and 24 months will be compared using paired samples t test. A 2-sided p-value < 0.05 will be considered statistically significant. All analyses will be performed using IBM SPSS Statistics version 23 (IBM, New York, NY). Figures will be generated using Graphpad Prism version 6 (Graphpad Prism, La Jolla, CA).

7. Direct access to source data and document

The investigator and the institution will permit trial-related monitoring, audits, EC review, and regulatory inspections (where appropriate) by providing direct access to source data and other documents (e.g. subjects' case sheets, blood test reports, X-ray reports, histology reports etc).

8. Ethics and regulatory approvals

The trial will be conducted in compliance with the principles of the Declaration of Helsinki (2013), the principles of GCP and in accordance with all applicable regulatory requirements. This protocol and related documents will be submitted for review to the Ethics Committee.

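### Every reduction depends on absence of proteinuria, but no urine protein is scheduled at the last three of six reductions (months 8, 9 and 10), including the steroid stop

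*Combined protocol and SAP*

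**What the plan says.** Section 5.1 (By visit) describes a stepwise withdrawal in which "each reduction is contingent on several factors". There are four conditions: stable eGFR, quiescent results on both Allosure and Trugraf, no de novo DSA, and "No proteinuria > 0.5 g/g creatinine on spot urine sample". The action column of the study timeline restates them in its header: "Action if stable renal function, immune quiescence, no de novo DSA, no proteinuria > 0.5 g/g". Failing any of them has a stated consequence: "If, at any point, a patient does not fulfill all of the abovementioned criteria, immunosuppression will not be (further) reduced".

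The timeline places the MMF/mTORi steps at months 1 and 4 and the prednisone steps at months 7, 8, 9 and 10, the last being the steroid stop. Urine protein is marked at inclusion and at months 1, 4, 7 and 12, and the text below the table adds month 24. The urine cells at months 8, 9 and 10 are blank. The list of tests done at every visit in Section 5.2 covers blood only; its routine item reads "Routine laboratory analyses, including complete blood count, basic metabolic panel, total protein, fasting glucose".

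Section 4.4 also halts weaning for new proteinuria above 0.5 g/g, but only once a second urine 2 to 4 weeks later confirms it. Section 5.1 has no confirmation step.

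**The concern.** The plan makes proteinuria a condition for every reduction but does not schedule the measurement at half of them. All three uncovered steps fall in the steroid taper, when MMF/mTORi has already been stopped, and they end at belatacept monotherapy.

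What is at stake is participant safety. Proteinuria that first appears between months 7 and 10 would not be seen by a scheduled urine until month 12, when no weaning step is left to halt. A high value then could still lead the principal investigator to return the patient to triple therapy, but it could not stop the taper. The same gap affects one of the two stated biopsy criteria in Section 5.1, proteinuria above 1.0 g/g on two urines: for a participant with a low month 7 value, no scheduled sample could start that criterion before month 12.

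**Working it through.** The plan gives no figure to reproduce. The check sets the visits with a reduction against the visits with each test.

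**Inputs** (months; inclusion = 0)
- Reductions, from the timeline: 1, 4, 7, 8, 9, 10.
- Urine protein, from the timeline and the text below it: 0, 1, 4, 7, 12, 24.
- Blood tests for eGFR, Allosure and Trugraf: monthly from 0 to 12.
- DSA, by the timeline and the text below it: 0, 3, 6, 9, 12, 24.
- DSA, by Section 5.2: "Donor-specific antibody screening occurs at 1, 4, 7, 10, 12 and 24 months".

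**Age of the latest scheduled sample** = month of the reduction minus month of the most recent scheduled test at or before it.

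| Reduction at month | 1 | 4 | 7 | 8 | 9 | 10 |
|---|---|---|---|---|---|---|
| Urine protein | 0 | 0 | 0 | 1 | 2 | 3 |
| eGFR, Allosure, Trugraf | 0 | 0 | 0 | 0 | 0 | 0 |
| DSA, timeline | 1 | 1 | 1 | 2 | 0 | 1 |
| DSA, Section 5.2 | 0 | 0 | 0 | 1 | 2 | 0 |

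**Results**
- Reductions without a same-visit urine: months 8, 9 and 10, so 3 of 6 reductions and 3 of the 4 steroid steps (7, 8, 9, 10).
- The month 7 urine is drawn at the visit where the taper starts, so it predates every steroid reduction. No urine is scheduled on any intermediate prednisone dose.
- At the steroid stop (month 10) the urine is 3 months old. At the other full drug stop (MMF/mTORi, month 4) it is 0 months old.
- Next scheduled urine after the stop: 12 − 10 = 2 months later.
- DSA is at most 2 months old at any reduction under either schedule, and is rechecked once during the taper: at month 9 by the timeline, at month 10 by Section 5.2. Under Section 5.2, the DSA condition at months 8 and 9 also rests on a month 7 sample.

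**Volume of added testing**, with all 20 participants reaching months 8 to 10
- Scheduled now: 6 × 20 = 120. Added: 3 × 20 = 60. Total 180, an increase of 60/120 = 50%.

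**Transient high values.** The documents give no rate. Let p be the assumed chance that a single urine is transiently above 0.5 g/g, independent between samples. Expected repeats = 60p. Participants with at least one affected step = 20 × [1 − (1 − p)³].

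| p | Repeats | 1 − (1 − p)³ | Participants of 20 |
|---|---|---|---|
| 2% | 1.2 | 5.9% | 1.2 |
| 5% | 3.0 | 14.3% | 2.9 |
| 10% | 6.0 | 27.1% | 5.4 |

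**The case against.** The best defence is that Section 5.1 never requires a same-visit urine. Using the latest available result is a natural reading, and a three-monthly rhythm (1, 4, 7) makes the oldest value used, 3 months, equal to the sampling interval. Nor is same-visit testing the plan's general standard: by the timeline, DSA has no same-visit sample at five of the six reductions. The month 7 urine also comes three months after MMF/mTORi stops, so it does inform on that withdrawal.

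This shows that the schedule can be followed as written. It does not cure the gap. The DSA condition is expressly worded to look back, "No appearance of any de novo DSA (at any MFI) at any previous point during study", and the proteinuria condition is not. Even if carry-forward was intended, the result carried forward predates the taper it is meant to guard. A strict three-monthly rhythm would also have placed a urine at month 10.

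Two further objections stand in part. Section 5.2 is weak corroboration, because it lists no urine test even for the visits where the timeline plainly schedules one. And the gap concerns scheduled samples only: an unscheduled urine is neither planned nor barred, patients attending clinic are examined monthly, and biopsy at the principal investigator's discretion is allowed.

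A reader might infer that the taper proceeds unmonitored, or that proteinuria is the only condition resting on month 7. The documents support neither. eGFR and both biomarkers are measured at every step, and under Section 5.2 DSA at months 8 and 9 rests on month 7 too.

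**Conclusion.** The point holds for scheduled testing. At 3 of 6 reductions, including the steroid stop, the proteinuria condition has no current scheduled measurement. It falls back on a sample 1, 2 or 3 months old that was taken before any steroid reduction, so scheduled urines cannot detect proteinuria emerging during the taper in time to halt it. The safeguard is weakened in one of its inputs and is not absent.

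The counts rest only on nominal visit months. The size of the risk is unknown: the documents do not say how often proteinuria would appear in this window without a change in eGFR, dd-cfDNA, Trugraf or DSA. It would go too far to conclude that participants will be harmed. The change is worth making because the plan already chose this condition for every step and the missing tests fit existing monthly contacts.

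**What to change.** 1. In the timeline, mark urine protein at months 8, 9 and 10; at minimum at month 10, before steroids stop.
2. In Section 5.2, list a spot urine protein/creatinine for all urine visits: inclusion and months 1, 4, 7, 8, 9, 10, 12 and 24. Listing only the new visits would create a fresh inconsistency.
3. For home-infusion patients, add urine collection at the local laboratory. Section 5.1 mentions only blood for them: "they will have blood samples (clinical and research specimens) drawn at their local Quest laboratory".
4. In Section 5.1, state that a value above 0.5 g/g pauses the step, and ends weaning only if a repeat 2 to 4 weeks later confirms it, in line with Section 4.4. Section 5.1 now has neither a confirmation nor a resume rule. Read literally, one transient value could end the wean and lower the percentage converted to monotherapy, which is a trial objective. Adding tests without this rule would make that more likely.

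Cost: up to 60 extra spot urines at existing monthly contacts, plus repeats, some of which may fall between contacts. At assumed per-sample transient rates of 2%, 5% or 10%, about 1, 3 or 6 repeats would be needed and about 1, 3 or 5 of 20 participants would have a step delayed. The minimum version, month 10 only, adds 1 × 20 = 20 urines but leaves months 8 and 9 resting on month 7.

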Like calcineurin inhibitors, belatacept is generally prescribed as part of an immunosuppressive regimen that includes either mycophenolic acid (MMF) or and mTOR inhibitor (mTORi) and steroids. Clinical experience suggests that in a significant proportion of belatacept-treated patients, MMF, mTORi and/or steroids can be reduced or even stopped, likely because they have reached a state of partial immunological tolerance. However, true personalization of immunosuppressive therapy, i.e. delivering the minimum amount of immunosuppression necessary to prevent kidney graft rejection for any given patient, is not yet possible because of a lack of reliable tests to monitor the degree of alloimmune reactivity in a kidney graft. So-called protocol biopsies are useful in this respect, but are invasive and suffer from sampling bias and inter-observer variability.

Several non-invasive immune monitoring tools have recently been developed that may aid in the personalization of immunosuppressive therapy. Two in particular are the focus of the current study. First, the presence of donor-derived cell-free DNA (dd-cfDNA) in the blood of kidney transplant recipients has been demonstrated to reflect graft injury.³⁻⁶ Very high values are a strong predictor of antibody-mediated rejection and low values (<1%) exclude active rejection with a negative predictive value of up to 98%.⁷ Second, a blood-based gene expression array (Trugraf™) can predict subclinical rejection in stable allografts with a negative predictive value of 78-88%.⁸

Whether patients with both dd-cfDNA levels < 1% and a Trugraf profile compatible with a state of immunological quiescence can safely undergo a reduction in the intensity of their immunosuppressive regimen has not been explored. In the current study, this hypothesis will be tested in belatacept-treated patients because they have a relatively high a priori likelihood of being in a state of immunological quiescence, which is also reflected by low rejection rates (<1%) after the first posttransplant year.⁹

3. Trial objectives and Design

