3.3 Primary endpoint at 24 months

- Occurrence of biopsy-proven acute rejection

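### Rejection counts only if a biopsy is done, and the plan has no class for participants who stop weaning or return to triple therapy without one

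*Combined protocol and SAP*

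**What the plan says.** Section 3.3 gives one primary endpoint, "Occurrence of biopsy-proven acute rejection", at 24 months. Section 4.4 ties it to the Banff 2017 criteria, so an event needs histology. The study timeline in section 5.1 schedules blood samples, urine protein and DSA, but no surveillance or end-of-study biopsy.

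Each reduction in section 5.1 depends on several conditions, among them: "Renal function is stable, defined as eGFR no more than 20% lower compared to value at inclusion". Section 4.4 lists what stops further weaning. Besides BPAR itself, the list has:
- "Decrease in eGFR > 20% from baseline without alternative explanation", confirmed on repeat testing;
- "Occurrence of new proteinuria > 0.5 g/g creatinine, confirmed on repeat urine sample after 2-4 weeks";
- de novo DSA at any MFI;
- Allosure above 1%, or a Trugraf signature compatible with rejection.

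Section 5.1 lists two criteria for a kidney biopsy: "Unexplained decrease in eGFR > 40% from baseline value", and new proteinuria above 1.0 g/g on two separate samples. Below these, the principal investigator may still biopsy if rejection is thought likely. The examples given are a new DSA with proteinuria under 1 g/g, and Allosure above 3% with a 20% eGFR fall.

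When a condition for weaning fails, "the principal investigator will decide whether to continue with the reduced-intensity immunosuppressive regimen or revert back to conventional triple therapy". No biopsy is required before that decision.

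Section 6 names a normality test and paired t tests of eGFR and proteinuria. It gives no analysis of the primary endpoint and no rule for scoring a participant who triggers, reverts or is never biopsied.

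**The concern.** A participant can show signs that the protocol treats as reason enough to stop weaning, be put back on triple therapy, recover, and never have a biopsy. With a two-state endpoint and no scoring rule, that participant can only be counted as having no BPAR. The decision to biopsy and the decision to re-intensify rest with the same investigator, in a study with no comparison arm.

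Section 3.1 asks what percentage of patients can be safely converted to monotherapy, and BPAR is the primary measure of that safety. If several of the 20 participants leave the weaning path unbiopsied, a low BPAR proportion has two readings: rejection did not happen, or it was not looked for. The planned results would not let a reader tell which.

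**Working it through.** **1. The two sets of limits side by side (sections 4.4 and 5.1)**

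| Sign | Stops weaning | Listed biopsy criterion | Ratio |
|---|---|---|---|
| eGFR fall | > 20%, confirmed | > 40%, unexplained | 40/20 = 2.0 |
| New proteinuria | > 0.5 g/g, confirmed | > 1.0 g/g, two samples | 1.0/0.5 = 2.0 |
| De novo DSA | any MFI | none on its own | – |
| Allosure | > 1% | none on its own | – |
| Trugraf | rejection-type signature | none on its own | – |

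The factor of two applies to the first two rows only. For an assumed baseline eGFR of 60, weaning stops below 0.8 × 60 = 48 and the biopsy criterion is met below 0.6 × 60 = 36. Values from 36 to just under 48 stop weaning without meeting the listed criterion.

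**2. How such a participant is scored**

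The endpoint needs histology (3.3, 4.4), none is scheduled (5.1), and section 6 has no rule for missing histology. That the participant counts as *no BPAR* is an inference from these three facts. The documents do not state it.

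**3. Possible size**

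The only design figure is a sample size of 20. It comes without a target rate, power or precision, so there is nothing to reproduce. No expected trigger or biopsy rate is given either, so the understatement cannot be computed. Two illustrations, with all inputs assumed:

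- One BPAR and three unbiopsied reversions. Reported: 1/20 = 5% (exact 95% CI 0.1 to 24.9%). If all three were rejections: (1 + 3)/20 = 20% (5.7 to 43.7%).
- True risk r, with a fraction d of rejections biopsied. P(no BPAR observed) = (1 − r·d)^20. For r = 20%, full detection gives 0.80^20 = 1.2% and d = 0.5 gives 0.90^20 = 12.2%. For r = 10%, the chance rises from 0.90^20 = 12.2% to 0.95^20 = 35.8%.

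**4. Whether counting every trigger gives an upper bound**

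It does not. Both tests are drawn monthly for 12 months, giving 2 × 12 = 24 results per participant after inclusion, and either test can trigger at any point. Assume specificity of 95 to 98% per result, independence and no true rejection. The chance of at least one false trigger is then 1 − 0.98^24 = 38% to 1 − 0.95^24 = 71%, or about 8 to 14 of 20. Conversely, participants who never trigger are also unbiopsied, so rejection among them would still be missed.

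**5. Ascertainment in months 13 to 24**

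The endpoint runs to 24 months, but section 5.2 places the laboratory visits with both biomarker tests in the first 12 months. In year two the plan has routine monthly laboratory work, with proteinuria and DSA checked for the study only at month 24. Most triggers are therefore not scheduled in that year.

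**The case against.** A lower threshold for pausing a taper than for an invasive procedure is a legitimate clinical design choice. The two sets of limits do not contradict each other. This stands, and nothing here asks for either to be moved.

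The discretionary clause in section 5.1 allows a biopsy below the criteria and gives combinations of abnormalities as examples. It narrows the gap. But it is optional, has no fixed rule, and does not say how a participant is scored when it is not used.

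A participant back on triple therapy has plainly not reached monotherapy, and eGFR, proteinuria, DSA and graft survival are secondary endpoints. So part of the information will appear elsewhere. However, the proportion safely converted is an objective without a defined endpoint, and none of the secondary endpoints shows how many participants had rejection left unresolved.

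Counting all triggers as events could swamp the result with false positives, as step 4 of the working shows. This stands. It is why such a count can serve only as a labelled sensitivity figure, and why triggers should be split by type.

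A reader might infer that the bias can only favour safety. The documents do not support that. Prompt re-intensification may truly prevent rejection, which is an effect of the monitored strategy, and biomarker-prompted discretionary biopsies can raise detection.

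**Conclusion.** The point holds in a limited form. As written, the BPAR proportion describes rejection found by for-cause biopsy. It can understate rejection, and it cannot separate *prevented* from *not looked for*. This rests on one inference, that unbiopsied participants count as event-free in the absence of any rule. The size is unknown, and the 5% against 20% contrast is an illustration with assumed counts.

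Two stronger readings should not be drawn:

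- Section 2 says that Trugraf "can predict subclinical rejection in stable allografts with a negative predictive value of 78-88"%, and a reader might turn this into 12 to 22% missed rejection, or 2.4 to 4.4 of 20. That figure concerns patients whose test was negative, whereas the point here concerns those who trigger. It also comes from another setting, while this cohort is selected for no prior rejection, no DSA and dd-cfDNA below 1%.
- A reader might infer that the endpoint cannot see subclinical rejection at all. The discretionary biopsy clause means that some could be found, so the supportable statement is that detection is incomplete and not governed by a rule.

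The matter goes beyond missing detail, because it decides what a low BPAR count can be said to show. It should be changed.

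**What to change.** Change the wording and the reporting only. No threshold, biopsy rule or treatment decision is altered.

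1. In sections 3.3 and 6, name the endpoint for-cause BPAR.
2. Classify each participant as *BPAR*, *no BPAR* or *rejection not excluded*. The third class is a section 4.4 trigger met, or a return to triple therapy, without a biopsy showing no rejection.
3. Report the third class by trigger type, with reversion to triple therapy shown separately.
4. Beside the BPAR proportion, give one figure that counts unbiopsied reversions as events and a second that counts all unbiopsied triggers. Label both as sensitivity figures, not upper bounds, for the reasons in step 4 of the working.
5. Report the proportion who reach and stay on monotherapy without BPAR.
6. Limit conclusions to clinically detected rejection, and note that most triggers are not scheduled in months 13 to 24.
7. Record Trugraf results and regimen changes explicitly in the study spreadsheet. Section 9 names Allosure results as held in the medical record, but names neither of these.

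The cost is a few extra recorded fields, some added text and results rows, and a companion figure less favourable than the BPAR proportion alone. No extra biopsies are needed.
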